### **5.7.2 Discontinuation from Sipuleucel-T Treatment**

Subjects who are unable to, or refuse to, undergo leukapheresis or receive at least 1 partial sipuleucel-T infusion should discontinue sipuleucel-T treatment.

Subjects who have received at least 1 partial ( $> 0$  mL) infusion of sipuleucel-T may discontinue sipuleucel-T without the requirement to discontinue radium-223. These subjects will continue all protocol-specified assessments in the active phase.

Any toxicity requiring sipuleucel-T discontinuation will be recorded as an AE in the subject's medical record and on the CRF.

### **5.7.3 Discontinuation from Radium-223 Treatment**

Radium-223 administration may be delayed by no more than four weeks for recovery of adverse events. In case of a treatment delay greater than four weeks, treatment should be discontinued. It is important to note that in general (unless otherwise agreed), in cases where study drug has been ordered, the time window is reduced to -3 days to + 3 days, due to decay. If administration has to be postponed more than 3 days after drug has been ordered, replacement of the drug order is required. Dose reduction for radium-223 will not be permitted and subjects with any toxicity requiring radium-223 dose reduction must discontinue radium-223 treatment.

Any toxicity requiring radium-223 discontinuation will be recorded as an AE in the subject's medical record and on the CRF.

### **5.7.4 Study Termination**

The whole study may be discontinued at the discretion of the investigator in the event of any of the following:

- Occurrence of AEs not seen previously which by virtue of their nature, severity and duration are considered to necessitate study termination.
- Hematologic adverse events criteria for study termination
  - $>2$  events of grade  $\geq 3$  thrombocytopenia or neutropenia in the first 10 subjects
  - $>3$  events of grade  $\geq 3$  anemia in the first 10 subjects
- Medical or ethical reasons affecting the continued performance of the study.
- Bayer is unable to provide radium-223 for the subject.
- Dendreon is unable to manufacture sipuleucel-T in  $> 2$  of first 10 patients.

Version 4.0 Date: 08/21/2020

NCT02463799

The values for radium-223 in this protocol has been revised as per the US NIST standardization update (agreed on 17 Mar 2015)

- Difficulties in the recruitment of patients.

## 5.8. Lost to Follow-Up

If the subject fails to respond to requests for follow-up, the clinical trial site will send a registered letter, at a minimum, to the subject requesting contact with the clinic. All attempts to resume contact (including copies of written correspondence) will be included in the source documentation. Subjects who do not respond to requests for follow-up after all reasonable attempts to establish contact will be considered “lost to follow-up”. Subjects who are lost to follow-up will be followed by the investigator for survival every 3 months using the SSDI and the NDI. Date of death, where available, will be recorded in the subject’s medical record and on the CRF.

## 5.9 Disease Progression

Disease progression is determined by the investigator per the definition below. The earliest date of disease progression will be recorded in the subject’s medical record and on the CRF. Following disease progression, all study treatments will cease, the subject will undergo a post-treatment visit and will be treated at the investigator’s discretion.

### 5.9.1 PSA Progression

Any 1 or more of the following events constitutes PSA progression:

- PSA Progression based on Prostate Cancer Working Group 2 (PCWG2) criteria [1]:
  - Decline from baseline: the first PSA increase that is  $\geq 25\%$  and  $\geq 2$  ng/mL above the nadir, and which is confirmed by a second value 3 or more weeks later (i.e., a confirmed rising trend).
  - No decline from baseline: PSA progression  $\geq 25\%$  and  $\geq 2$  ng/mL after 12 weeks from baseline.

PSA measurements obtained during the treatment should not be used as the sole criterion for determining progression. Study treatments may be continued in equivocal cases where there is PSA progression but no clear evidence of disease progression or clinical deterioration, and where the investigator feels the subject is deriving clinical benefit from the study treatments and subject safety is not compromised.

### 5.9.2 Clinical and Radiographic Progression

#### 5.9.2.1 Clinical Progression

Version 4.0 Date: 08/21/2020

NCT02463799

The values for radium-223 in this protocol has been revised as per the US NIST standardization update (agreed on 17 Mar 2015)

- New spinal cord or nerve root compression.
- New pathologic fracture.
- Use of opioid analgesics for cancer-related pain

#### **5.9.2.2 Radiographic Progression**

- Disease progression based on radiographic imaging based on RECIST and PCWG2 criteria for soft tissue and bone, respectively.

### **6.0 STUDY ASSESSMENTS AND PROCEDURES**

#### **6.1. Schedule of Assessments**

a. Arm 1: sipuleucel-T and radium-223

	Screen a	Rad-1 b	Rad-2	PreL-1 c	Sip-1	Rad-3	PreL-2 c	Sip-2	PreL-3 c	Sip-3	Rad-4		Rad-5		Rad-6					F/U e	
	Im-1											Im-2 d		Im-3 d		Im-4 d	Im-5 d	Im-6 d	Im-7 d		
	Week	0	4	6 c	6	8	8 c	8	10 c	10	12	12 d	16	16 d	20	20 d	32 d	45 d	58 d		
Informed consent	X																				
Registration/	X																				
Pathology	X																				
Rad-223 infusion		X	X			X					X		X		X						
Sip-T infusion					X			X		X											
Clinical Assessments																					
Medical History	X																				
P/E	X	X	X	X		X	X		X		X		X		X		X	X	X		
Vital Signs	X	X	X	X	X f	X	X	X f	X	X f	X	X	X	X	X	X	X	X	X	X	
ECOG PS	X	X	X	X		X	X		X		X	X	X	X	X	X	X	X	X	X	
Imagingg	X												X				X	X	X	X h	
Safety Assessment																					
AEs/SAEs		X	X	X	X	X	X	X	X	X	X	X	X	X	X	X	X	X	X	X	X i
Medication																					
Anticancer Tx	X	X	X	X		X	X		X		X		X		X		X	X	X	X	
1 st Opioid use	X	X	X	X		X	X		X		X		X		X	X	X	X	X	X	
Survival Status																					
Lab Assessments																					
Hematology	X	X	X	X		X	X		X		X		X		X		X	X	X		
Chemistry/ LDH/ magnesium/phosphorus	X	X	X	X		X	X		X		X		X		X		X	X	X		
Testosterone	X																				
PSA	X												X				X	X	X		
Coagulation l	X																				
Immune Assessments																					
Dendreon j	X											X		X		X	X	X	X		
JH Lab k	X			X												X			X		

Version 4.0 Date: 08/21/2020

NCT02463799

The values for radium-223 in this protocol has been revised as per the US NIST standardization update (agreed on 17 Mar 2015)

Abbreviations: AE = adverse event; A/P = abdomen/pelvis; CT = computed tomography; ECOG = Eastern Cooperative Oncology Group; F/U = follow up visit; Im = Immune assessment visit; JH = Johns Hopkins; MRI = magnetic resonance imaging; PAP = prostatic acid phosphatase; P/E = physical exam; PET = positron emission tomography; Sip = sipuleucel-T infusion visit; PS = performance status; PreL = preleukapheresis visit; PSA = prostatic specific antigen; Rad = radium-223 infusion visit; SAE = serious adverse event; Tx = treatment

- a. All screening procedures must occur within 28 calendar days prior to registration, with the exception of written informed consent, histological documentation of prostate cancer with Gleason grading, and imaging for confirmation of metastatic disease
- b. Radium-223 visits will occur 6 times at weeks 0, 4, 8, 12, 16, and 20
- c. Applies to all leukapheresis; pre-leukapheresis visits will occur  $\leq 5$  days prior to each leukapheresis. First sipuleucel-T infusion may occur any time between the second and third radium-223 infusion.
- d. At baseline, week 6, 10, 14, 26, 39, and 52 post-first sipuleucel-T infusion
- e. Follow-up visits will occur at every 3 months after week 58 visit for additional 1 year or until the subject's death
- f. Vital signs will be measured 1 to 30 minutes prior to, and at 30 minutes ( $\pm 10$  min) following each infusion
- g. Bone scan and CT or MRI abdomen/pelvis
- h. Per institution's standard procedure/at the investigator's discretion
- i. Only treatment-related events will be collected
- j. Baseline sample can be drawn at subject's "day one visit" (prior to dosing). See Appendix 1 for sample preparation instructions.
- k. Blood samples for antigen spread analysis will be collected at baseline (can be drawn at subject's "day one visit" (prior to dosing) , 1st pre-leukapheresis visit, and weeks 14 and 52 post-first sipuleucel-T infusion.
- l. PTT, PT/INR

## b. Arm 2: sipuleucel-T alone

	Screen a Im-1	PreL-1 b	Sip-1	PreL-2 b	Sip-2	PreL-3 b	Sip-3	Im-2 c	Im-3 c	Im-4 c	Im-5 c	Im-6 c	Im-7 c	F/U d
Week	Week	0	0	2	2	4	4	6 c	10 c	14 c	26 c	39 c	52 c	
Week														
Informed consent	X													
Registration/	X													
Pathology	X													
Sip-T infusion			X		X		X							
Clinical Assessments														
Medical History	X													
P/E	X	X		X		X								
Vital Signs	X	X	X e	X	X e	X	X e	X	X	X	X	X	X	
ECOG PS	X	X		X		X		X	X	X	X	X	X	
Imagingf	X									X	X	X	X	X g
Safety Assessment														
AEs/SAEs		X	X	X	X	X	X	X	X	X	X	X	X	X h
Medication														
Anticancer Tx	X	X		X		X								X
1 st Opioid use	X	X		X		X								X
Survival Status														
Lab Assessments														
Hematology	X	X		X		X								
Chemistry/ LDH/ magnesium / phosphorus	X	X		X		X								
Testosterone	X													
PSA	X								X		X	X	X	
Coagulation k	X													
Immune Assessments														
Dendreon l	X							X	X	X	X	X	X	
JH Lab j	X									X			X	

Version 4.0 Date: 08/21/2020

NCT02463799

The values for radium-223 in this protocol has been revised as per the US NIST standardization update (agreed on 17 Mar 2015)

Abbreviations: AE = adverse event; A/P = abdomen/pelvis; CT = computed tomography; ECOG = Eastern Cooperative Oncology Group; F/U = follow up visit; Im = Immune assessment visit; JH = Johns Hopkins; MRI = magnetic resonance imaging; PAP = prostatic acid phosphatase; P/E = physical exam; PET = positron emission tomography; Sip = sipuleucel-T infusion visit; PS = performance status; PreL = preleukapheresis visit; PSA = prostatic specific antigen; SAE = serious adverse event; Tx = treatment

- a. All screening procedures must occur within 28 calendar days prior to registration, with the exception of written informed consent, histological documentation of prostate cancer with Gleason grading, and imaging for confirmation of metastatic disease
- b. Applies to all leukapheresis; pre-leukapheresis visits will occur  $\leq 5$  days prior to each leukapheresis
- c. At baseline, week 6, 10, 14, 26, 39, and 52 post-first sipuleucel-T infusion
- d. Follow-up visits will occur at every 3 months after week 58 visit for additional 1 year or until the subject's death
- e. Vital signs will be measured 1 to 30 minutes prior to, and at 30 minutes ( $\pm 10$  min) following each infusion
- f. Bone scan and CT or MRI abdomen/pelvis
- g. Per institution's standard procedure/at the investigator's discretion
- h. Only treatment-related events will be collected
- i. Baseline sample can be drawn at subject's "day one visit" (prior to dosing). See Appendix 1 for sample preparation instructions.
- j. Blood samples for antigen spread analysis will be collected at baseline (can be drawn at subject's "day one visit" (prior to dosing), and weeks 14 and 52 post-first sipuleucel-T infusion.
- k. PTT, PT/INR

## 6.2 Registration

After eligibility screening, patients who are selected to participate will be registered with the study site/institution. A record of patients who fail to meet entry criteria (ie, screen failures) will be maintained by each individual site. Patient registration must be complete before beginning any treatment or study activities.

Prior to protocol enrollment and initiation of treatment, subjects must sign and date an IRB-approved consent form. To register a patient, the following documents must be completed and faxed or emailed to the Lead Center Program Coordinator:

- Signed patient consent form
- Registration Form
- Copies of the prostate cancer pathology report, baseline laboratory studies including CBC with differential, liver and kidney function tests, testosterone, PSA, and CT/bone scan. Other materials may also be sent if considered pertinent for confirming patient eligibility.

The Lead Center will review the documents to confirm eligibility. To complete the registration process the Lead Center will:

- Assign a patient study number
- Register the patient on the study with SKCCC's Clinical Research Office
- Fax or e-mail the patient study number to the participating site

## 6.3 Randomization

Eligible subjects will be registered and randomly assigned in a 1:1 ratio to receive 6 infusions of radium-223 and 3 infusions of sipuleucel-T starting after second dose of radium-223 (Arm 1) or 3 infusions of sipuleucel-T alone (Arm 2).

Arm 1: 6 infusions of radium-223 with 3 infusions of sipuleucel-T starting after second dose of radium-223

Arm 2: 3 infusions of sipuleucel-T

## 6.4 Demographics

Demographic information, including birth date, race and ethnicity will be recorded in the subject's medical record and on the CRF.

## 6.5 Clinical Assessments

Version 4.0 Date: 08/21/2020

NCT02463799

The values for radium-223 in this protocol has been revised as per the US NIST standardization update (agreed on 17 Mar 2015)

Clinical assessments will be performed at the times noted in Table 1.

### **6.5.1 Medical History**

Significant historic and current medical conditions or illness, allergies to medications, and prior surgical interventions will be recorded in the subject's medical record and on the CRF. Information regarding the subject's history of smoking and other risk factors for CVEs will also be recorded.

Symptoms that are ongoing at the time of, or that develop after the subject provides informed consent and before registration, will also be considered medical history.

Medical history will include the subject's 6 most recent PSA values, vaccinations in the two years prior to registration, and all prior anticancer therapies.

### **6.5.2 Physical Examination**

Physical examinations will be performed at the times noted in Table 1 and must be conducted by an appropriately qualified investigator listed on the Form FDA 1572.

The physical examinations conducted at screening and at pre-leukapheresis visits will include a review of the skin, pulmonary, cardiovascular, and neurologic systems, abdomen, and extremities. A review of additional body systems will be at the discretion of the investigator.

For all other visits that call for a physical examination, the body systems reviewed will be at the discretion of the investigator.

Each physical examination will include weight measurement. Height will be measured at screening only.

Abnormal physical examination findings at screening will be considered part of the medical history and will be recorded on the Medical History CRF. Any new or worsening physical examination findings identified after the subject's registration will be considered AEs and will be recorded in the subject's medical record and on the CRF.

### **6.5.3 Vital Signs**

Vital signs (respiration rate, temperature, heart rate, and blood pressure) will be measured at the times noted in Table 1. Vital signs will be recorded in the subject's medical record and on the CRF.

#### **6.5.4 ECOG Performance Status**

Eastern Cooperative Oncology Group performance status will be assessed at the times noted in Table 1. The assessment must be conducted by an appropriately qualified investigator listed on the Form FDA 1572. The ECOG performance status will be recorded in the subject's medical record and on the CRF.

#### **6.5.5 Imaging**

Subjects must have a bone scintigraphy test (bone scan) or Na-F PET or C11-acetate PET and CT or MRI scan of the abdomen and pelvis within 56 days prior to registration. If a bone scan is used, solitary lesions or lesions which could be attributed to causes other than metastatic prostate cancer must be confirmed with a second modality (i.e., CT or MRI).

When available, standard of care scans will be used to demonstrate metastatic disease at screening. If scans meeting the eligibility criteria are not available, scans may be obtained during the screening phase. If post-screening radiographic imaging is performed per standard of care to assess disease progression, the same modalities used at screening should be used.

### **6.6 Safety Assessments**

Safety assessments will be performed in conjunction with all visits as indicated in Table 1.

#### **6.6.1 Adverse Events and Serious Adverse Events**

Adverse events, including serious AEs (SAEs) will be assessed at all visits and as needed during the course of the study.

All non-serious AEs and SAEs, regardless of relationship to study treatment, will be collected from registration through the week 20 and will be recorded in the subject's medical record and on the CRF. Following week 20, only new treatment-related AEs and SAEs will be recorded.

Only treatment-related AEs and SAEs ongoing at week 20 visit will be followed by the investigator until resolution, return to baseline, or a determination by the investigator that no further improvement is expected.

See Section 7.0 for information regarding AE and SAE reporting.

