**Immune monitoring blood samples** will be drawn at screening and at 6, 10, 14, 26, 39, and 52 weeks after the first infusion of sipuleucel-T in both arms. Additional blood samples will be obtained at baseline, first pre-leukapheresis visit (only in Arm 1), and weeks 14 and 52 post the first infusion of sipuleucel-T for exploratory antigen spread assessment.

After last study research visit, safety, treatment-related AEs, survival status, PSA, first opioid use for cancer-related pain (if applicable), and anticancer therapies will be assessed every 3 months for additional 1 year or until the subject's death.

The study design is illustrated below.

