## 7.3 Adverse Events Reporting

The principal investigator will notify the appropriate regulatory agencies of any SAEs occurring during the study period, regardless of causality. These agencies include the Sidney Kimmel Comprehensive Cancer Center (SKCCC) Data and Safety Monitoring Committee (DSMC), and the Institutional Review Board (IRB) and the Institutional Biosafety Committee (IBC) of the Johns Hopkins Medical Institutions (JHMI). The representatives of Dendreon will also be notified. Expedited reporting to the PI within 24 hours is required for all SAEs (see Section 7.4.1). For SAEs that are fatal, life-threatening, or treatment-related but non-life threatening: IRB/IBC reporting by the PI is required within 3 days. For unrelated SAEs, IRB/IBC reporting

by the PI is required within 15 days. All other AEs should be documented on CRFs and submitted according to the standard data management guidelines.

Adverse event information will be collected continuously throughout the duration of the study. Participants will be instructed to notify their treating provider of any new signs or symptoms, and providers will actively assess patients for adverse events at each visit (including by evaluation of laboratory studies). The investigator will assess each AE for its severity and for its relationship to the study drug, and all events Grade 1 or higher will be documented on CRFs and then reported as described above within the required time frame. Any AE occurring while a patient is on study (*i.e.* after informed consent has been signed) or within 30 days of study termination requires reporting. AEs occurring later than this must still be reported if a causal relationship with the study drug is suspected.

For all AEs, the investigator must pursue and obtain information to adequately determine the causality and outcome of the event, and to assess whether it meets criteria for a SAE. In addition, follow-up of an AE is required until the event either resolves or stabilizes.

The principal investigator must keep copies of all CRFs and other AE information, including correspondence with the IRB and/or FDA, for as long as required to comply with national and international regulations.

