### **7.4.1 Serious Adverse Event Collection and Reporting**

All SAEs and unknown/unexpected reactions that occur from the signing of the study-specific consent through the duration of the post-therapy adverse event collection should be reported to the Study Coordinator, Dendreon Safety Manager, and Bayer Global Pharmacovigilance within 24 hours of being made aware of the SAE. If the Study Coordinator cannot be reached within 24

hours, the PI ([name] MD) should be contacted at [contact] or at [[contact]](mailto:[contact]). Notification can be made via phone or telefacsimile or email.

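### Section 6.6.1 stops all-cause adverse event recording at week 20 while Section 7.3 keeps it open to 30 days after study termination, and the adverse event tables start at a dose Arm 2 never receives

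*Combined protocol and SAP*

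**What the plan says.** Section 6.6.1 sets the narrow rule: "All non-serious AEs and SAEs, regardless of relationship to study treatment, will be collected from registration through the week 20". It continues: "Following week 20, only new treatment-related AEs and SAEs will be recorded". On follow-up it says: "Only treatment-related AEs and SAEs ongoing at week 20 visit will be followed by the investigator until resolution".

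Section 7.3 sets a wide rule: "Adverse event information will be collected continuously throughout the duration of the study". It adds that "all events Grade 1 or higher will be documented on CRFs", and that an event on study, counted from signed consent, or "within 30 days of study termination requires reporting". Suspected causality becomes a condition only after that. It also requires follow-up of every adverse event until it resolves or stabilises.

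Other places that bear on the window:

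- The synopsis (Study Design and Duration) describes the later phase this way: "After last study research visit, safety, treatment-related AEs, survival status". Section 3.0 repeats this and names week 58.
- In Section 6.1, the adverse event row is marked at visits through week 58 in Arm 1 and week 52 in Arm 2. The footnote restricting collection to related events is attached to the follow-up column.
- Section 7.4.1 asks for expedited reporting of the following: "All SAEs and unknown/unexpected reactions that occur from the signing of the study-specific consent through the duration of the post-therapy adverse event collection".
- For concomitant medications, Section 6.7 stops at week 20 and Section 5.5 at week 58.

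On analysis, Section 8.6.4.1 begins the adverse event tables at the first radium-223 infusion. Section 8.3 puts anyone with at least one leukapheresis or one radium-223 dose in the safety population. Section 8.6.4 calls for descriptive summaries in aggregate and names no table by arm.

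**The concern.** Safety of the combination is a secondary objective (synopsis and Section 2.2.2), and the randomised sipuleucel-T-alone arm is its natural comparator. If 6.6.1 and 7.3 disagree, two sites can each follow the protocol and return different adverse event data for the same kind of subject. Under 6.6.1, whether a later event is recorded depends on the investigator's causality call, and no blinding is described. The cut-off also falls at a different point relative to treatment in the two arms. A table start defined by radium-223 leaves Arm 2 events with no valid place in the summaries as written.

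**Working it through.** There is no stated figure to reproduce. The check compares the rules and then does week arithmetic on each arm's own schedule.

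**1. The rules side by side**

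| Place | Start | End of all-cause recording |
|---|---|---|
| 6.6.1 | registration | week 20 |
| 7.3 | consent | 30 days after study termination |
| 7.4.1 (SAEs) | consent | end of post-therapy collection, no week given |
| Synopsis and 3.0 | not stated | implied: last research visit |
| 6.1 schedules | first visit after screening | implied: week 58 (Arm 1), week 52 (Arm 2) |

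The 6.6.1 and 7.3 rows contradict each other directly. Saying that one governs collection and the other reporting does not resolve it, because 7.3 itself speaks of collection and of documentation on CRFs. The two sections also differ on follow-up of ongoing events.

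**2. Inputs from Section 6.1**

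- Arm 1: radium-223 at weeks 0, 4, 8, 12, 16 and 20; sipuleucel-T at weeks 6, 8 and 10; last research visit at week 58.
- Arm 2: sipuleucel-T at weeks 0, 2 and 4; later visits at weeks 6, 10, 14, 26, 39 and 52. None falls at week 20, although 6.6.1 refers to a visit in that week.

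**3. Weeks in dispute** (last research visit minus 20)

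- Arm 1: 58 − 20 = 38; 38/58 = 65.5%.
- Arm 2: 52 − 20 = 32; 32/52 = 61.5%.

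These are maxima, for subjects who reach the last visit.

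**4. All-cause recording after the last scheduled infusion**

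- Under 6.6.1: Arm 1, 20 − 20 = 0 weeks; Arm 2, 20 − 4 = 16 weeks.
- To the last research visit: Arm 1, 58 − 20 = 38 weeks; Arm 2, 52 − 4 = 48 weeks.

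The Arm 1 zero moves a little with the visit window. Section 5.7.3 generally narrows the window to 3 days either side once drug is ordered, so dose six could fall on day 140 − 3 = 137. If week 20 is counted to its last day (day 146), that leaves at most 146 − 137 = 9 days. With the one-week delay-free window of Section 3.0 (7 days either side) it would be 146 − 133 = 13 days. A delay allowed by 5.7.3 would put the dose after a fixed week-20 cut-off.

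**5. Do the scheduled end points match across arms?** Counted from the first sipuleucel-T infusion, Arm 1 ends at 58 − 6 = 52 weeks and Arm 2 at 52 − 0 = 52 weeks. They match.

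**6. Table start.** Arm 2 receives no radium-223 (Section 6.3), so the start in 8.6.4.1 is undefined for it. With 1:1 allocation and 33 (synopsis) or 34 (Section 8.2) enrolled, that is about 16 to 17 subjects.

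**The case against.** Several parts of the opposing case stand.

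- A reader might infer that 7.4.1 also contradicts the week-20 end. It names no end week, and 6.6.1 may itself define the post-therapy period. The explicit difference is the start point (consent against registration); the end-point conflict is an inference.
- Marks in the schedules do not prove all-cause recording, since 6.6.1 also has events assessed at every visit. The evidence there is the footnote's placement. It is clear in Arm 2; in Arm 1 the extracted row has more marks than columns. The design text lists what is assessed after the last visit and does not say outright that all-cause recording runs until then. These places support the wider window but do not establish it alone.
- Week 20 appears in both 6.6.1 and 6.7 and coincides with the last scheduled radium-223 visit, so it may be deliberate. The contradiction with 7.3 remains either way.
- The contrast of about 0 and 16 weeks depends on the anchor. Arm 1 still has 20 weeks from its first radium-223 dose and 20 − 10 = 10 weeks after its last scheduled sipuleucel-T infusion. If the cut-off is the visit itself, it may move with a delayed dose.
- A reader might take the aggregate wording in 8.6.4 to mean that the arms will be pooled. The text does not say so; it is ambiguous and needs clarifying.
- A reader might also infer that Arm 2 events go uncollected. They do not: 6.6.1 collects them from registration. The fault in 8.6.4.1 is in the table definition.

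The consequence is also bounded. Section 7.2 reserves the unrelated category for events clearly due to other factors. Related events, deaths within 30 days of last treatment (7.5) and clinically significant laboratory results (7.6) keep a reporting route. SAEs do too, insofar as the 7.4.1 period extends past week 20.

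**Conclusion.** Two defects hold as written. First, 6.6.1 and 7.3 give incompatible windows for all-cause adverse event recording. The design text, the footnote placement, the matching split between 5.5 and 6.7 and the missing week-20 visit in Arm 2 all favour the longer window. Second, the table start in 8.6.4.1 does not exist for the sipuleucel-T-alone arm, about half of randomised subjects.

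The time in dispute is up to 38 of 58 weeks in Arm 1 and 32 of 52 weeks in Arm 2. This assumes that week 20 is counted on each arm's own schedule and that the subject reaches the last research visit; withdrawal or progression shortens it. These are weeks of observation. It is tempting to read the percentages as the share of safety events lost, but the documents give no event rates from which to estimate that. Mainly non-serious events judged unrelated are at risk.

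Safety is descriptive with no formal testing, and the primary immune endpoint and its power are unaffected. The correction is still worthwhile, because following the text literally yields inconsistent data and an undefined table.

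**What to change.** - Reconcile 6.6.1, including its reference to a week-20 visit, with 7.3 and the schedules. Use one all-cause window in both arms. The end point best supported by the design text and schedules is the last research visit already planned (week 58 in Arm 1, week 52 in Arm 2), with related events only in the follow-up phase.
- State one start point, consent or registration, for 6.6.1, 7.3 and 7.4.1. Say what the 30-day rule in 7.3 means for a subject who leaves early, and give the 7.4.1 collection period an end.
- Align the concomitant-medication windows in 5.5 and 6.7 in the same edit.
- In 8.6.4.1, replace the table start with one that exists in both arms: for example registration, randomisation, or the earlier of first leukapheresis and first radium-223 dose. The last option matches the safety population in 8.3.
- In 8.6.4, state that descriptive safety summaries are shown by treatment arm, with observation time, because the windows run 58 and 52 weeks from week 0.

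The cost is protocol wording, somewhat more adverse event recording at existing visits, and tables by arm. No visit is added and treatment does not change. For subjects already past week 20, lost recording may not be recoverable, so the report must say which rule was followed.
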